## 4.9 Efficacy Evaluation

The disease progressions are based on the following criteria depending on specific module evaluation specifications.

### 4.9.1 Response using RECIST 1.1.

For modules requiring RECIST results, the RECIST tumour response data will be used to determine each participant’s visit response according to RECIST version 1.1. It will also be used to determine if and when a participant has progressed in accordance with RECIST 1.1.

Baseline radiological tumour assessments are to be performed no more than 28 days before the first dose/administration of study medication and ideally as close as possible to the start of study treatment. Tumour assessments are then performed every 8 weeks ( $\pm 1$  week) following start of study treatment up to 1 year, then every 12 weeks ( $\pm 1$  week) until objective disease progression.

If an unscheduled assessment is performed, and the participant has not progressed, every attempt should be made to perform the subsequent assessments at their scheduled visits. This schedule is to be followed in order to minimise any unintentional bias caused by some participants being assessed at a different frequency than other participants.

From the investigator’s review of the imaging scans, the RECIST 1.1 tumour response data will be used to determine each participant’s visit response according to RECIST version 1.1. At each visit, participants will be programmatically assigned a RECIST 1.1 visit response of CR, PR, SD or PD (see [Table 7](#)), using the information from target lesions (TLs), non-target lesions (NTLs) and new lesions and depending on the status of their disease compared with baseline and previous assessments. If a participant has had a tumour assessment which cannot be evaluated, then the participant will be assigned a visit response of not evaluable (NE) (unless there is evidence of progression in which case the response will be assigned as PD).

RECIST outcomes (i.e., PFS, ORR, etc.) will be calculated programmatically for the site investigator data from the overall visit responses.

### Table 7 : TL visit responses

Visit Responses	Description
Complete Response (CR)	Disappearance of all TLs. Any pathological lymph nodes selected as TLs must have a reduction in short axis to < 10 mm.
Partial response (PR)	At least a 30% decrease in the sum of diameters of TLs, taking as reference the baseline sum of diameters, as long as criteria for PD are not met.
Progressive disease (PD)	A $\geq 20\%$ increase in the sum of diameters of TLs and an absolute increase of $\geq 5$ mm, taking as reference the smallest sum of diameters since treatment started including the baseline sum of diameters.
Stable disease (SD)	Neither sufficient shrinkage to qualify for PR nor sufficient increase to qualify for PD
Not Evaluable (NE)	Only relevant in certain situations (i.e. if any of the target lesions were not assessed or not evaluable or had a lesion intervention at this visit; and scaling up could not be performed for lesions with interventions). Note: If the sum of diameters meets the progressive disease criteria, progressive disease overrides not evaluable as a target lesion response
Not applicable (NA)	No TLs are recorded at baseline

**Target Lesions (TLs) – site investigator data**

Measurable disease is defined as having at least one measurable lesion, not previously irradiated, which is  $\geq 10$  mm in the longest diameter (LD) (except lymph nodes which must have short axis  $\geq 15$  mm) with computed tomography (CT) or magnetic resonance imaging (MRI) and which is suitable for accurate repeated measurements. A participant can have a maximum of 5 measurable lesions recorded at baseline with a maximum of 2 lesions per organ (representative of all lesions involved and suitable for accurate repeated measurement) and these are referred to as target lesions (TLs). If more than one baseline scan is recorded, then measurements from the one that is closest and prior to first dose/administration of study medication will be used to define the baseline sum of TLs. It may be the case that, on occasion, the largest lesion does not lend itself to reproducible measurement in which circumstance the next largest lesion, which can be measured reproducibly, should be selected.

All other lesions (or sites of disease) not recorded as TL should be identified as NTLs at baseline. Measurements are not required for these lesions, but their status should be followed at subsequent visits.

Note: For participants who do not have measurable disease at entry (i.e., no TLs) but have non-measurable disease, evaluation of overall visit responses will be based on the overall NTL assessment and the absence/presence of new lesions. If a participant does not have measurable disease at baseline, then the TL visit response will be not applicable (NA).

***Rounding of TL data***

For calculation of PD and PR for TLs percentage changes from baseline and previous minimum should be rounded to 1 decimal point before assigning a TL response.

For example, 19.95% should be rounded to 20.0% but 19.94% should be rounded to 19.9%.

***Missing TL data***

For a visit to be evaluable all TL measurements should be recorded. However, a visit response of PD should still be assigned if any of the following occurred:

- A new lesion is recorded
- An NTL visit response of PD is recorded
- The sum of TLs is sufficiently increased to result in a 20% increase, and an absolute increase of  $\geq 5$  mm, from nadir even assuming the non-recorded TLs have disappeared.

Note: the nadir can only be taken from assessments where all the TLs had a LD recorded.

If there is at least one TL measurement missing and a visit response of PD cannot be assigned, the visit response is NE.

If all TL measurements are missing, then the TL visit response is not evaluable (NE). Overall visit response will also be NE, unless there is a progression of non-TLs or new lesions, in which case the response will be PD.

***Lymph nodes***

For lymph nodes, if the size reduces to  $< 10$  mm then these are considered non-pathological. However, a size will still be given, and this size should still be used to determine the TL visit response as normal. In the special case where all lymph nodes are  $< 10$  mm and all other TLs are 0mm then although the sum may be  $>0$  mm the calculation of TL response should be over-written as a CR.

***TL visit responses subsequent to CR***

A CR can only be followed by CR, PD or NE. If a CR has occurred, then the following rules at the subsequent visits must be applied:

- Step 1: If all lesions meet the CR criteria (i.e. 0mm or  $< 10$ mm for lymph nodes) then response will be set to CR irrespective of whether the criteria for PD of TL is also met i.e. if the sum of diameters for lymph node short axis increases by 20% but all lymph node TL remain  $< 10$ mm.
- Step 2: If some lesion measurements are missing but all other lesions meet the CR criteria (i.e. 0mm or  $< 10$  mm for lymph nodes) then response will be set to NE irrespective of whether, when referencing the sum of TL diameters, the criteria for PD are also met.
- Step 3: If not all lesions meet the CR criteria (i.e., a pathological lymph node is selected as TL has short axis  $\geq 10$  mm or the reappearance of previously disappeared lesion) or a new lesion appears, then response will be set to PD.

- Step 4: If after steps 1 – 3, a response still cannot be determined will be set to remain as CR.

### ***TL too big to measure***

If a TL becomes too big to measure this should be indicated in the database and a size ('x') above which it cannot be accurately measured should be recorded. If using a value of x in the calculation of TL response would not give an overall visit response of PD, then this will be flagged and reviewed by the study team. It is expected that a visit response of PD will remain in the vast majority of cases.

### ***TL too small to measure***

If a TL becomes too small to measure, then this will be indicated as such on the eCRF and a value of 5mm will be entered into the database and used in TL calculations. However, a smaller value may be used if the radiologist has not indicated 'too small to measure' on the case report form and has entered a smaller value that can be reliably measured. If a TL response of PD results (at a subsequent visit) then this will be reviewed by the study team.

### ***Irradiated lesions/lesion intervention***

Previously irradiated lesions (i.e. lesion irradiated prior to entry into the study) should be recorded as NTLs and should not form part of the TL assessment.

Any TL (including lymph nodes), which has had intervention during the study (for example, irradiation / palliative surgery / embolisation), should be handled in the following way and once a lesion has had intervention then it should be treated as having intervention for the remainder of the study noting that an intervention will most likely shrink the size of tumours:

- Step 1: the diameters of the TLs (including the lesions that have had intervention) will be summed and the calculation will be performed in the usual manner. If the visit response is PD this will remain as a valid response category.
- Step 2: If there was no evidence of progression after step 1, treat the lesion diameter (for those lesions with intervention) as missing and if  $\leq 1/3$  of the TLs have missing measurements then scale up as described in the 'Scaling' section below. If the scaling results in a visit response of PD then the participant would be assigned a TL response of PD.
- Step 3: If, after both steps, PD has not been assigned, then, if appropriate (i.e., if  $\leq 1/3$  of the TLs have missing measurements), the scaled sum of diameters calculated in step 2 should be used, and PR or SD then assigned as the visit response. Participants with intervention are evaluable for CR as long as all non-intervened lesions are 0 (or  $<10$  mm for lymph nodes) and the lesions that have been subject to intervention have a value of 0 (or  $<10$  mm for lymph nodes) recorded. If scaling up is not appropriate due to too few non-missing measurements, then the visit response will be set as NE.

At subsequent visits the above steps will be repeated to determine the TL and overall visit response. When calculating the previous minimum, lesions with intervention should be treated as missing and scaled up (as per step 2 above).

**Scaling**

- If > 1/3 of TL measurements are missing (because of intervention) then TL response will be NE, unless the sum of diameters of non-missing TL would result in PD (i.e. if using a value of 0 for missing lesions, the sum of diameters has still increased by 20% or more compared to nadir and the sum of TLs has increased by  $\geq 5$  mm from nadir).
- If  $\leq 1/3$  of the TL measurements are missing (because of intervention) then the results will be scaled up (based on the sizes at the nadir visit) to give an estimated sum of diameters and this will be used in calculations; this is equivalent to comparing the visit sum of diameters of the non-missing lesions to the nadir sum of diameters excluding the lesions with missing measurements.

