#### 4.17.3 Progression free Survival (Cohort A)

PFS is defined as the time from first dose until the date of objective disease progression or death (by any cause in the absence of progression) regardless of whether the participant withdraws from study therapy or receives another anti-cancer therapy prior to progression (i.e. date of PFS event or censoring – date of first dose + 1). Participants who have not progressed or died at the time of analysis will be censored at the time of the latest date of assessment from their latest evaluable RECIST

assessment. However, if the participant progresses or dies after two or more missed visits, the participant will be censored at the time of the latest evaluable RECIST 1.1 assessment prior to the two missed visits. NE is not considered a missed visit.

Given the schedule of RECIST assessments (i.e., every 8 weeks for the first year and every 12 weeks there after until a confirmed progression) two missing visits will equate to 18 weeks in the first year (i.e.,  $2 \times 8 = 16$  weeks + 1 week for early assessment + 1 week for a late assessment = 18 weeks), 26 weeks in the subsequent years (i.e.,  $2 \times 12 = 24$  weeks + 1 week for early assessment + 1 week for a late assessment = 26 weeks) after the first treatment allowing for early and late visits.

If the participant has no evaluable visits or does not have baseline data, they will be censored at Day 1 unless they die within 17 weeks (16 weeks plus 1 week allowing for a late assessment within the visit window).

The PFS time will always be derived based on scan/assessment dates and not visit dates.

RECIST assessments/scans contributing towards a particular visit may be performed on different dates. The following rules will be applied:

- For investigational assessments, the date of progression will be determined based on the **earliest** of the dates of the component that triggered the progression
- When censoring a participant for PFS the participant will be censored at the **latest** of the dates contributing to a particular overall visit assessment

Note: for TLs only the latest scan date is recorded out of all scans performed at that assessment for the TLs and similarly for NTLs only the latest scan date is recorded out of all scans performed at that assessment for the NTLs.

Analyses of PFS will be based upon the molecularly eligible centrally confirmed set and safety analysis set.

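### The scaled-up target-lesion sum is not equivalent to a like-for-like comparison on the 5 mm criterion, so PD can be called on less than 5 mm of measured growth when the remaining lesions' nadir sum is under 25 mm

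*SAP*

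**What the plan says.** All of this is in SAP section 4.9.1.

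- Table 7 defines target-lesion PD by a 20% or greater "increase in the sum of diameters of TLs and an absolute increase of" at least 5 mm. Both conditions must be met. The comparison is made by "taking as reference the smallest sum of diameters since treatment started including the baseline sum of diameters".
- Under the heading on irradiated lesions and lesion intervention, Step 1 sums all target lesions at their measured size, and PD on that sum stands. If there is no PD, Step 2 treats the locally treated lesions as missing and, where at most one third are missing, scales up. "If the scaling results in a visit response of PD then the participant would be assigned a TL response of PD".
- Under Scaling, the branch for at most one third missing works from the lesions' nadir sizes "to give an estimated sum of diameters and this will be used in calculations". The same sentence then adds that "this is equivalent to comparing the visit sum of diameters of the non-missing lesions to the nadir sum of diameters", where the treated lesions are left out of that nadir.
- The lesion-intervention text and the worked example that follows Scaling both carry scaled sums forward into the nadir used for later visits.
- Under the rule for lesions too small to measure, a 5 mm value is entered, and a later target-lesion PD goes to study-team review.

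**The concern.** The sentence gives one instruction (use the scaled sum) and then says that it equals another (compare the measured lesions with their own nadir). PD has a relative and an absolute criterion, and a change of scale leaves the first alone but not the second. A programmer who codes the scaled sum and one who codes the comparison it is said to equal can therefore assign different visit responses to the same data.

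The SAP derives visit responses programmatically, so this wording becomes code. Target-lesion PD makes the overall visit response PD. That response feeds best response, confirmation of CR or PR, PFS in Cohort A, rPFS in Cohort B, and duration of response. Small nadir sums, where the two bases part, are most likely in participants whose tumours have shrunk.

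**Working it through.** **The SAP's own figure.** The worked example scales 26 cm at the visit by 29.3/26.8: 26/26.8 × 29.3 = 28.43, which reproduces the stated 28.4 cm. This requires 29.3 cm to be the nadir sum of all target lesions, although the text describes it as a measure of lesion 5. The relative change is 28.43/29.3 − 1 = −2.99% on the scaled basis and 26/26.8 − 1 = −2.99% on the measured basis. The absolute change is −0.87 cm scaled and −0.80 cm measured. The example thus already shows equivalence on percentage and not on millimetres.

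**General form.** Let S be the nadir sum of the remaining (measured, untreated) lesions, A the nadir sum of all target lesions, and g the measured growth of the remaining lesions.

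- Scaled sum = (S + g) × A/S
- Relative change of the scaled sum = g/S, the same as on the measured lesions
- Absolute change of the scaled sum = g × A/S, larger than g because A > S

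The least measured growth that gives PD is:

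- scaled basis: max(0.2S, 5S/A)
- measured basis: max(0.2S, 5 mm)

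If S is 25 mm or more, 0.2S is at least 5 mm and both rules reduce to 0.2S. If S is below 25 mm, the measured rule needs 5 mm and the scaled rule needs less.

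**Which participants.** With at most five target lesions, at most one third missing means exactly one treated lesion out of three, four or five.

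**Illustration.** Nadir is 10+10+10 mm, one lesion is treated, and the others go to 12+12 mm.

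- Step 1: PD needs a total of 1.2 × 30 = 36 mm, so the treated lesion would have to measure at least 36 − 24 = 12 mm. Below that, Step 2 applies.
- Step 2, scaled: 24 × 30/20 = 36 mm against 30 mm, which is +20% and +6 mm: PD.
- Comparison said to be equivalent: 24 mm against 20 mm, which is +20% and +4 mm: not PD.

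**Range.** Lesion sizes are assumptions, chosen within the SAP's measurement rules.

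| Remaining lesions at nadir (mm) | Treated lesion at nadir (mm) | S | A | Least growth for PD, scaled (mm) | Least growth for PD, measured (mm) |
|---|---|---|---|---|---|
| 10+10 | 10 | 20 | 30 | 4.0 | 5.0 |
| 10+10 | 30 | 20 | 50 | 4.0 | 5.0 |
| 7+8 | 20 | 15 | 35 | 3.0 | 5.0 |
| 5+5 | 10 | 10 | 20 | 2.5 | 5.0 |
| 5+5 | 15 | 10 | 25 | 2.0 | 5.0 |
| 15+15 | 15 | 30 | 45 | 6.0 | 6.0 |
| 10+10+10 | 10 | 30 | 40 | 6.0 | 6.0 |

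In the last two rows S exceeds 25 mm and the bases agree.

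**The case against.** The best defence is that Table 7 sets the 5 mm criterion on the sum of all target lesions, and the scaled sum estimates exactly that. Had all three 10 mm lesions been assessable and each grown by 20%, 30 to 36 mm would have been PD. On this view the operative instruction is clear and the equivalence clause is loose commentary. Part of this stands: applying 5 mm to the scaled sum is a choice one could make, so a PD reached that way is not wrong in itself. But the SAP cannot make that choice and also say that it equals the like-for-like comparison, since the two give different calls.

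The defence is also right that the reach is narrow. The 20% criterion is unaffected, and nothing changes once S reaches 25 mm. The 2 mm cases need remaining lesions of about 5 mm each. Where those are too-small-to-measure entries, study-team review already covers the resulting PD. That review does not cover the 10+10+10 mm case.

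A reader might infer that the branch for more than one third missing has the opposite fault, because PD there is assigned only "if using a value of 0 for missing lesions, the sum of diameters has still increased by 20% or more compared to nadir". With two 30 mm lesions and one removed, the other would need 1.2 × 60 = 72 mm, against 36 mm like-for-like. Since "NE is not considered a missed visit", progression might then be dated late. The SAP does not support calling this an error:

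- No equivalence is claimed for that branch.
- Zero for the missing lesions with NE as the default is a conservative rule, and it matches the SAP's rule for missing target-lesion data.
- The remaining lesions have to more than double only if they hold less than 60% of the nadir sum (1.2/0.6 = 2). Through Step 1, for two equal lesions, the treated one must also measure less than 40% of its nadir size (2.4 − 0.4 = 2.0).
- Non-target progression or a new lesion still gives overall PD.

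**Conclusion.** The point holds for the branch with at most one third of target lesions missing, and only for the 5 mm criterion. The stated equivalence is false there, and it changes PD calls when the remaining lesions sum to less than 25 mm at nadir: PD is then possible on 2 to 4 mm of measured growth in the cases shown, against 5 mm on the comparison the SAP names. It should not be read as a fault in both branches.

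The number of participants affected is not given and is assumed to be small. For scale, one changed responder is 1/25 = 4.0 percentage points in Cohort A and 1/27 = 3.7 points in Cohort B. That is the weight of one participant, not a forecast. The effect on response rates also assumes that the local treatment does not itself count as subsequent cancer therapy, since responses after such therapy are excluded anyway. Cohort A PFS runs regardless of other therapy, so its progression date is exposed either way.

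**What to change.** For PD in the branch with at most one third missing, require both the 20% and the 5 mm increase on the sum of the measured, untreated lesions, against the smallest earlier sum of those same lesions. State that reference explicitly, because the visit with the smallest total need not be the one with the smallest sum of the remaining lesions. Keep the scaled sum for assigning PR or SD, and limit the equivalence clause to percentage change.

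Align three other places: Step 2 and the previous-minimum sentence under lesion intervention, and the nadir sentence after the scaling example. Otherwise PD would be judged on measured sums while those places still define a scaled nadir. Leave the branch for more than one third missing as it is.

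The cost is a few sentences in the SAP and a small programming change. The drawback is that PD after local treatment rests on fewer lesions. If the sponsor prefers the scaled sum for the 5 mm test, saying so and restricting the equivalence clause would remove the contradiction, but PD on less than 5 mm of measured growth would remain possible.

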**Example of scaling:**

Lesion 5 is missing at the follow-up visit; it had a BL measure of 29.3 cm. The sum of lesions 1-4 at the follow-up is 26 cm. The sum of the corresponding lesions at nadir visit is 26.8 cm.

Scale up as follows to give an estimated TL sum of 28.4 cm:

$$\frac{26}{26.8} \times 29.3 = 28.4 \text{ cm}$$

CR will not be allowed as a TL response for visits where there is missing data. Only PR, SD or PD (or NE) could be assigned as the TL visit response in these cases. However, for visits with  $\leq 1/3$  lesion assessments not recorded, the scaled-up sum of TLs diameters will be included when defining the nadir value for the assessment of progression.

**Lesions that split in two**

If a TL splits in two, then the LDs of the split lesions should be summed and reported as the LD for the lesion that split.

**Lesions that merge**

If two TLs merge, then the LD of the merged lesion should be recorded for one of the TL sizes and the other TL size should be recorded as 0 cm.

**Change in method of assessment of TLs**

CT, MRI and clinical examination are the only methods of assessment that can be used within a trial, with CT and MRI being the preferred methods and clinical examination only used in special cases. If a change in method of assessment occurs between CT and MRI this will be considered acceptable and no adjustment within the programming is needed.

If a change in method involves clinical examination (e.g., CT changes to clinical examination or vice versa), any affected lesions should be treated as missing.

